## **8 Research Question and Objectives**

This study addresses the research question of whether vaccinations with new licenced COVID-19 vaccines, (Comirnaty, Moderna, AstraZeneca's and Janssen and subsequently

approved vaccines in the EU during the data collection), are effective in reducing the burden of COVID-19 in Spain in comparison with no vaccination periods.

**Primary objective** is to evaluate the effectiveness of each COVID-19 vaccine in reducing the covid-19 infections (confirmed through test and regardless the prognosis and clinical phenotype (i.e. whether symptomatic or asymptomatic, mild or severe).

**Secondary objectives** of this study will be splitting the effectiveness

- by the following outcomes:
  - asymptomatic (defined as a positive test (whether PCR or antigens) without recorded symptoms in primary care +/-14days of the date the sample was taken). Note: In epidemiological vigilance protocols, among asymptomatic patients, isolation must be maintained till 10 days after the date when the sample was taken.
  - symptomatic (defined as positive test (whether PCR or antigens) with recorded symptoms in primary care or Hospitalisations/Intensive care unit (ICU) admissions +/-14days of the date the sample was taken (or at anytime linked with the test result))
  - Hospitalisations/Intensive care unit (ICU) admissions for COVID-19 at anytime linked with the test result or within +/-14days of the date the sample was taken (if hospitalisation was recorded in primary care clinical profile)
  - All-cause mortality as a recorded death with COVID 19 listed as an underlying cause of death on cause-of-death registers, or a death during a hospitalisation, with COVID-19 as a listed diagnosis, or a death within a specified time period (e.g., 28 days) after a diagnosis or hospitalisation for COVID 19.
- over clinically meaningful subgroups (old people; patients with cardiovascular disease, diabetes, or chronic pulmonary disease, chronic renal impairment, treated cancer, patients with a history of transplantation, Down Syndrome found linked with the prognostic of the covid-19 infection; as well as smoking, males and obesity suspected linked with the prognosis in some studies)
- along the time since complete vaccination (up-to 3 months, 6 months and ever after).

A feasibility evaluation will be conducted before the start of the study to evaluate the availability of key data elements and the appropriateness of the study design.

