## 4 Abstract

**Title:** Real-world effectiveness of different COVID-19 vaccines in Spain: a cohort study based in primary health care (BIFAP) and linked data sources

**Rationale and background:** Multiple vaccine candidates for COVID-19 are progressing through development and testing with anticipated widespread adoption and use after approval. The real-world effectiveness of these vaccines must be evaluated in populations in Spain.

**Research question and objectives:** To evaluate the effectiveness of all COVID-19 vaccines administered in Spain in reducing the medically attended diagnosis of COVID-19 in any setting (confirmed through test and regardless the prognosis and clinical phenotype)

Secondary objectives of this study will be splitting the effectiveness

- by the following outcomes:
  - asymptomatic (defined as a positive test (whether PCR or antigens) without recorded symptoms in primary care +-14days of the date the sample was taken). Note: In epidemiological vigilance protocols, among asymptomatic patients, isolation must be maintained till 10 days after the date when the sample was taken.
  - symptomatic (defined as a positive test (whether PCR or antigens) with recorded symptoms in primary care or Hospitalisations/Intensive care unit (ICU) admissions +-14days of the date the sample was taken (or at anytime linked with the test result))
  - Hospitalisations/Intensive care unit (ICU) admissions for COVID-19 at anytime linked with the test result or within +-14days of the date the sample was taken (if hospitalisation was recorded in primary care clinical profile)
  - All-cause mortality as linked with the test result or within +-14days of the date the sample was taken (if hospitalisation was recorded in primary care clinical profile)
- over clinically meaningful subgroups (old people; patients with cardiovascular disease, diabetes, or chronic pulmonary disease, chronic renal impairment, treated cancer, patients with a history of transplantation, Down Syndrome found linked with the prognostic of the covid-19 infection; as well as smoking, males and obesity suspected linked with the prognosis in some studies)
- along the time since complete vaccination (3 months, 6 months and ever after).

**Study design:** This is an observational cohort study to compare the occurrence of covid-19 infection among unvaccinated and vaccinated individuals.

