#### **9.3.3.2 Symptomatic or Asymptomatic Diagnosis of COVID-19**

In a secondary analysis, in order to inform about the effectiveness to protect against asymptomatic and symptomatic infections, outcomes from the main analysis will be divided according to the symptoms recorded around the date of confirmed covid-19 in the patient PC eHR. Two effectiveness parameter, i.e. to protect against asymptomatic and asymptomatic infection, will be estimated separately for each vaccine. The date of the COVID cases will be the 1st date the sample was taken for testing.

Cases of **Asymptomatic** infection will be defined as a positive test without recorded symptoms in primary care  $\pm$ 14days, hospitalisations/Intensive care unit (ICU) or hospital diagnosis of the date the sample was taken). In asymptomatic analysis, symptomatic infections will participate as non-cases stopping at covid date.

Cases of **Symptomatic** infection will be defined as a positive test with recorded symptoms in primary care  $\pm$ 14days of the date the sample was taken, or linked Hospitalisations/Intensive care unit (ICU) admissions. In symptomatic analysis, asymptomatic infections will participate as non-cases stopping at covid date.

Note: In epidemiological vigilance protocols, among asymptomatic patients, isolation must be maintained till 10 days after the date when the sample was taken. For a sensitive approach we will broaden till 14 days in order to allow for delayed records in PC eHR.

\*Note: some misclassification may be present since patients with mild disease (mild symptoms) may never seek care that will be assumed as asymptomatic.

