### **9.3.3.4 COVID-19–Specific Mortality**

The data availability on the cause of death will depend on the region providing the data to BIFAP, thus the primary outcome of COVID-19–specific mortality will have the following hierarchical definition

- A recorded death with COVID-19 listed as an underlying cause of death on cause-of-death registers
- Death during a hospitalisation, with COVID-19 as a listed diagnosis
- Death within a specified time period (e.g., up-to 8 weeks [73]) after a diagnosis or hospitalisation for COVID-19

The date of the outcome will be the date of death.

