### **9.3.3.5 All-Cause Mortality**

Cause-of-death information in BIFAP may be lacking depending on the region providing data; therefore, all-cause mortality will be used as a secondary outcome. All-cause mortality will be defined as a recorded patient death in primary care, or hospital records during the outcome ascertainment period of up-to 8 weeks after the date of the COVID date for main analysis (the 1st date the sample was taken for testing as recorded in the lab registries linked to PC eHR if available). The date of the outcome will be the date of death.

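### Section 8 labels COVID-19-specific mortality as all-cause mortality, and three sections define all-cause mortality differently

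*Protocol*

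**What the plan says.** Four places in the protocol define a mortality outcome.

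- **Abstract (Section 4), secondary objectives:** "All-cause mortality as linked with the test result or within +-14days of the date the sample was taken". A parenthesis about hospitalisation follows; the same one closes the hospitalisation bullet just above.
- **Section 8, secondary objectives:** "All-cause mortality as a recorded death with COVID 19 listed as an underlying cause of death on cause-of-death registers", or an in-hospital death with COVID-19 among the diagnoses, or "a death within a specified time period (e.g., 28 days) after a diagnosis or hospitalisation for COVID 19".
- **Section 9.3.3.4:** "the primary outcome of COVID-19–specific mortality will have the following hierarchical definition". Its limbs are the three of Section 8, the last now reading "Death within a specified time period (e.g., up-to 8 weeks [73]) after a diagnosis or hospitalisation for COVID-19".
- **Section 9.3.3.5, all-cause mortality:** a death recorded in primary care or hospital "during the outcome ascertainment period of up-to 8 weeks after the date of the COVID date for main analysis". The reason given is that cause of death may be missing in some regions.

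The split by symptoms also differs between sections. In the Abstract and Section 8, an asymptomatic case is a positive test "without recorded symptoms in primary care +/-14days of the date the sample was taken", while a symptomatic case has either primary-care symptoms or an admission. Section 9.3.3.2 additionally requires, for an asymptomatic case, no "hospitalisations/Intensive care unit (ICU) or hospital diagnosis of the date the sample was taken", and treats each class as a non-case in the analysis of the other.

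**The concern.** Mortality is a stated secondary objective, and an objective should point to one set of events. Here the name used in Section 8 belongs to one outcome in 9.3.3.5, while the events listed under it belong to another in 9.3.3.4. Whoever programs the outcome from the objectives and whoever programs it from the outcome section will count different deaths and report both as all-cause mortality.

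The choice also reaches the competing-risk analysis. Section 9.7.3.3 gives death from causes other than COVID-19 as its example of a competing event. Under some of these definitions such a death is itself the outcome.

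Finally, every version needs a COVID-19 record of some kind. A reader who sees all-cause mortality in the results would expect deaths without any such record to be included.

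**Working it through.** The protocol gives no event count or power figure for mortality, so there is nothing to reproduce. The check applies each definition to the same example deaths.

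**Inputs.** Time limits are ±14 days from the sample (Abstract, second limb), 28 days from diagnosis or hospitalisation (Section 8, third limb, given as an example), up to 8 weeks from the same point (9.3.3.4, third limb, also an example), and up to 8 weeks from the COVID date (9.3.3.5). Eight weeks is 8 × 7 = 56 days. The Abstract's linked limb and the first two limbs of Section 8 and 9.3.3.4 have no time limit.

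For the examples, day 0 is both the sample date and the diagnosis date. For the day-20 and day-40 deaths there is no later admission.

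| Death | Abstract | Section 8 | 9.3.3.4 | 9.3.3.5 |
|---|---|---|---|---|
| Day 20, unrelated cause, outside hospital, not linked with the test | No (20 > 14) | Yes (20 ≤ 28) | Yes, if the hierarchy reaches its last limb (20 ≤ 56) | Yes (20 ≤ 56) |
| Day 40, otherwise the same | No (40 > 14) | No (40 > 28) | Yes, if the last limb is reached (40 ≤ 56) | Yes (40 ≤ 56) |
| Day 70, COVID-19 registered as underlying cause | Only if linked | Yes (first limb) | Yes (first limb) | No (70 > 56) |
| No COVID-19 test, diagnosis, hospitalisation or cause-of-death record | No | No | No | No |

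The three columns that carry the all-cause name (Abstract, Section 8, 9.3.3.5) disagree in each of the first three rows. The disagreement runs both ways: 9.3.3.5 is wider than Section 8 at day 40 and narrower at day 70. The last row shows that none of them is all-cause in the usual sense.

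**Follow-up.** Section 9.3.3 assesses outcomes during follow-up. Section 9.3.1 ends follow-up at the stop date and lists COVID-19 infection among the stop criteria. Its wording takes the latest of the listed criteria, whereas 9.3.3.2 and 9.3.3.3 end the contribution of non-cases at the COVID date. If infection ends follow-up, the deaths after infection that 9.3.3.4 and 9.3.3.5 are built to count fall outside it. No section says that mortality is an exception.

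**Symptom classes.** Let S be symptoms recorded in primary care within ±14 days, and H an admission that meets the symptomatic definition. All cases have a positive test.

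| S | H | Abstract and Section 8 | Section 9.3.3.2 |
|---|---|---|---|
| No | No | Asymptomatic | Asymptomatic |
| Yes | No | Symptomatic | Symptomatic |
| Yes | Yes | Symptomatic | Symptomatic |
| No | Yes | Both | Symptomatic |

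Only the last row overlaps, and 9.3.3.2 resolves it.

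**The case against.** The best defence is that Section 9.3.3 is the operational text and the Abstract and objectives are summaries. A careful programmer would follow 9.3.3, where the two mortality outcomes have separate names and the symptom classes do not overlap. All the outcomes concerned are secondary. The primary objective in Section 8 and the main outcome in 9.3.3.1 are both laboratory-confirmed infection, so the word primary in 9.3.3.4 can be read as ranking the two mortality outcomes against each other.

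Much of this stands, and it limits the point. It does not remove it: Section 8 is not an abbreviated form of 9.3.3.5 but a full statement of a different outcome under the same name. Nor does following 9.3.3 settle the window in 9.3.3.4, which is only an example, or the stop rule.

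Several stronger readings are tempting but not supported:

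- **That windows of 14, 28 and 56 days translate into shares of deaths captured.** The 14 and 28 days are single limbs beside limbs with no time limit, and the documents give no distribution of time to death.
- **That tying all-cause mortality to a positive test defeats its purpose of avoiding testing bias or exposing healthy-vaccinee bias.** Section 9.3.3.5 states only one purpose, to cope with missing cause of death. Counting any death after confirmed infection is consistent with that.
- **That COVID-19-specific mortality is absent from the objectives.** The hierarchy is in Section 8; only its name is missing.
- **That admitted cases in general are counted twice.** Only those without primary-care symptoms in the ±14-day span are, and only under the Abstract and Section 8.

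**Conclusion.** The contradiction is real. One secondary outcome name covers three different sets of events, and in Section 8 it is attached to the outcome that 9.3.3.4 calls COVID-19-specific. The mortality result would depend on which section is followed. How many deaths would change status cannot be derived from the documents.

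The primary analysis is untouched. The overlap of asymptomatic and symptomatic cases is a lesser matter of aligning summary text with 9.3.3.2. The conclusion rests on the definitions as written, with the two example windows taken at their stated values.

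**What to change.** 1. In the Abstract and Section 8, list two separately named secondary outcomes that match 9.3.3: COVID-19-specific mortality (the 9.3.3.4 hierarchy) and death from any cause after confirmed COVID-19 (the 9.3.3.5 outcome, renamed accordingly). Give both the same fixed window in every section, in place of the examples.
2. State in 9.3.1 that, for mortality outcomes, follow-up continues past the infection date although infection is a stop criterion.
3. If a true all-cause outcome is wanted, add it as any recorded death, with follow-up not ended by infection. Without that condition it could drop the deaths after infection.
4. Replace the word primary in 9.3.3.4, since Section 8 and 9.3.3.1 reserve that place for laboratory-confirmed infection.
5. Align the asymptomatic definition in the Abstract and Section 8 with 9.3.3.2.

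Most of this is protocol wording. Item 2 is a change of rule, and item 3 would add an outcome. The data specification must then include deaths after infection and, for item 3, deaths without any COVID-19 record. The protocol is dated 20 April 2021 and Section 6 starts data collection at the end of June 2021, so the timetable leaves room to settle this before extraction.

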## **9 Research Methods**

### **9.1 Study Design**

An observational cohort study of people prioritized for covid-19 vaccination will be implemented to allow for the estimation of effect measures on the absolute scale

(incidence difference) (e.g., time point-specific difference) [10] and relative scale (e.g., time point-specific risk ratios, hazard ratios, and vaccine effectiveness measures). The occurrence of covid-19 infection among unvaccinated and vaccinated patients will be compared as defined below.

This study primarily describes an approach to the retrospective collection of data to using BIFAP data (and linked registry by patient's level) after the necessary data have accumulated (real-time; expected every 2 months starting in 21st December 2021).

The choice of an exchangeable comparator group is a key factor in ensuring a valid study design and addressing confounding. In the current protocol, individuals not yet receiving COVID 19 vaccines will be pooled for a random selection among those with matched criteria to the vaccinated individuals. We have discarded to select the following control groups due to the reason explained below:

- Identified at receipt of a different vaccine such as influenza: the period of influenza vaccination (September-December) seems to be fewer circulation covid-19 since fewer incidences were reported. Thus, they may not be comparable
- During a general practitioner visit: will not be as frequent or representative or a normal non-pandemic situation when people are able to visit the health setting without any restriction. Thus, they may not be comparable
- Choosing a fixed time unit (weeks for instance) to create a series of nested cohorts, each starting at each new time unit [20,21]. Similar to the selected option, this one is valid and although more precise it is more complicated to implement. Also, the variance estimation would need to be adjusted accordingly (e.g., by bootstrapping) because individuals are allowed to contribute to multiple study cohorts [22].

The inclusion and exclusion criteria for the study cohort and thus for the selection of comparative groups are described in the following sections.

### **9.1.1 Study Feasibility Stage**

The feasibility of conducting a vaccine effectiveness study in BIFAP (electronic health records (eHR; i.e. secondary data) will be evaluated regarding:

1. data availability and data validity (Sections 9.1.1.1, 9.1.1.2, and 9.1.1.3)
2. valid study design (Section 9.1.1.4) during final protocol development.

### **9.1.1.1 Availability of Required Data Elements**

We will determine that all data elements for the implementation of the study, including co-variates (see Section 9.3), inclusion and exclusion criteria (Section 9.2), vaccinations, covid-outcomes, and potential confounders (Sections 9.1.1.5 and 9.3.4) are available.

### **9.1.1.2 Validity of COVID-19 Test results and Diagnosis Coding**

In this study, COVID-19 outcomes will be identified from the lab test results linked with PC eHR by the regional parties before sending to BIFAP to create its common data model.

#### **COVID-19 Test results (PCR, antigens, etc.)**

Test results for coronavirus will be linked with PC eHR. For effectiveness analysis, cases will be positive covid infections recorded in that registry that may be confirmed through positive PCR, Antigens or any other confirmatory criteria established by clinical protocols (that definition is out of the scope of the current study).

Laboratory-confirmed infection is considered gold-standard to identify cases for the main analysis, thus no predictive values will be estimated. As explained below, identification of so-called 'possible' covid cases recorded only through diagnosis coding (without lab information) will be performed in a Sensitivity analysis (Section 9.7.4.2).

Also, an estimation of the concordance between the observed incidences in BIFAP and those 'expected' will be performed (i.e. external validation) as a proxy for the accurateness to identify cases in BIFAP and discussion of potential reasons if differences would be present.

The 'expected' cumulative incidences will be calculated by dividing the COVID cases reported daily to RENAVE (base de datos de vigilancia epidemiológica; by calendar period, region and age) by the population reported in the Spanish National Statistics Institute for that year [73]. Access to RENAVE will be available by one of the institution collaborating in the current study [74].

### **9.1.1.3 Validity of Vaccine Exposure**

The precision and sensitivity of COVID-19 vaccine records included in the BIFAP's Table of Vaccine are not known. However, high precision and sensitivity have been estimated for other vaccinations recorded in that table

- after manual revision (against free text comment for human papillomavirus vaccination)(2) or
- validated against expected coverages (as in the Spanish recommended schedules) or external sources (such as other European countries with public

vaccination programs) for vaccinations against human papillomavirus, pertussis, influenza or meningococcus (3).

The information about the COVID vaccinations included in that Table is the result of linking all vaccination registries with the public PC eHR. That link has been strongly recommended (and it is compulsory) by the Ministry of Health and it is used by the Ministry to provide the official coverages since the vaccination campaigns started.

Vaccination data for each patient will include the vaccination date, dose, name of the vaccine, brand and batch for each jab.

Even though, the vaccinations records of the initial priority population for vaccination (i.e. frontline health and social care workers, residents in a care home and patients with special needs) will be available in BIFAP, we will not study them since we expect not enough quality criteria of the baseline consultations to the PCP. Thus, as aforementioned the current study will be restricted to populations where both, vaccination status and baseline and updated clinical history, can be accurately identified.

#### **9.1.1.4 Definition of Time Zero**

In studies of vaccinated versus unvaccinated persons, researchers must determine the appropriate time point at which to identify patients and begin follow-up. Aligning the evaluation of eligibility criteria, covariate assessment, exposure assignment, and beginning of follow-up (time zero) avoids selection bias and immortal person-time bias and addresses a well-defined study question [13].

Time zero is the time when the vaccination status is assigned; all eligibility criteria must be fulfilled at that point, and COVID outcomes must start to be counted at that point [14].

Time zero in the vaccinated group will be the date when the 1st dose of COVID-19 vaccine is administered (i.e. recorded). That date will be also used for the unvaccinated pairs as Time zero.

The aim of the **Main analysis** will be the estimation of the effectiveness  $\geq 15$  days after full vaccination series whether 1- or 2-doses regimens (and regardless of delayed completion of 2-dose vaccine series ,i.e. recorded dates will be accepted as real world data even though the time between doses are not fully adjusted to recommended intervals). Analysis will be performed by vaccine brand.

In order to properly observe the moment when the effect of the vaccination starts, the period between 1st Dose and 14 days after the 2nd dose will be divided and compared with unvaccinated patients. Thus, at least 5 cut-of periods will be identified along each patient's follow-up contribution:

- 1) Non-exposed period among Unvaccinated patients (Reference for Effectiveness estimation)

- 2) D1-induction time: up-to 14 days after 1st dose
- 3) D1-effectiveness: 15 days after 1st dose to 2nd dose
- 4) D2-induction time: up-to 14 days after 2nd dose
- 5) D2-effectiveness in the short run: 15-90 days after 2nd dose
- 6) D2-effectiveness in the medium run: 91-180 days after 2nd dose
- 7) D2-effectiveness in the long run:  $\geq 181$  days after 2nd dose

[figure not shown]

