## 9.5 Study Size

All patients meeting the eligibility criteria in BIFAP will be included as source population. BIFAP includes information of around 7.7 million patients aged  $\geq 18$  years (as last updated version in 2018), which distribution by sex and age is as follows:

	TOTAL	18 - 19	20 - 24	25 - 29	30 - 34	35 - 39	40 - 44	45-49	50 - 54	55-59	60-64	65-69	70-74	75-79	80-84	85-89	90-110
TOTAL	7720843	252143	424740	465933	526002	647688	747020	717918	702323	658868	569616	493770	454787	350359	317844	246643	145189
Women	3991612	122805	209807	232836	265565	324008	369475	357547	352106	330858	290309	255848	242742	194252	187908	154500	101046
Men	3729231	129338	214933	233097	260437	323680	377545	360371	350217	328010	279307	237922	212045	156107	129936	92143	44143

Taking into account the estimated COVID vaccine effectiveness reported in clinical trials [75-78], varying assumptions of vaccine unexposed to exposed ratio, anticipated global sample sizes of patients aged  $\geq 18$  years in BIFAP, a cumulative positive symptomatic COVID cases of 60,57 per 100,000 people in 14-days in Spain (as reported on 22 March 2021 [when started the vaccination for general people, i.e. apart from health workers and nursing home residents] in [www.cnecovid.isciii.es/covid19/](http://www.cnecovid.isciii.es/covid19/)), [33], the different probabilities that the upper limit of the 95% CI of the risk ratio (RR) being below 1.00 (a correlate of the lower bound of the vaccine effectiveness estimate being above 0.00 [Section 9.7.3.1] demonstrating a protective effect of vaccination) was estimated and displayed in Table 1:

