## **9.7.4 Subgroup, Sensitivity, and Exploratory Analyses**

### **9.7.4.1 Conducting Subgroup Analyses**

The primary analyses will be stratified by clinically meaningful subgroups found or suspected linked with the prognostic of the covid-19 infection, which will include the following:

- Old patients (i.e. aged  $\geq 80$  years)
- Patients with cardiovascular disease,
- Patients with diabetes,
- Patients with chronic pulmonary disease (COPD, asthma, etc);
- Patients with cancer
- Patients who are immunocompromised
- Pregnant women
- Smoker patients (suspected linked with the prognosis in some studies)
- Patients with obesity (BMI for obese category)
- Patients vaccinated against Influenza in the fall-winter season 2020-2021 this analysis seeks to reduce unmeasured confounding by health care access, adherence to recommendations, and preventive health care behaviours [9,25].
- Geographic region (if sufficient sample size in all regions)

Also, the primary analyses will be stratified by calendar months in order to observe in periods with stronger confusion due to individuals prioritisation (i.e. channelling of atypical patients in the period immediately following approval [44]). For instance, confusion could be strongest when the vaccinations occurred only for health care workers and nurse home residents. Background anamnesis may not be systematically recorded in primary care for those groups and we do not have information about the job or nursing home residing for selecting non-vaccinated individuals based on those criteria (or matching by it), thus the compared unvaccinated cohort may have less probability of vaccination or outcome, respectively.

Stratifying by months, we could observe differences in effectiveness that could be affected by a higher confusion in months previous to the date when vaccination was recommended for a broad general population.

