## **9.9 Limitations of the Research Methods**

Although this protocol addresses many design considerations to avoid common biases of vaccine effectiveness research, studies of COVID-19 vaccines may be subject to many of the limitations common to non-randomised studies based in existing health care data.

Patient's test-seeking behaviour may be associated with both severity of infection symptoms and personal health-seeking behaviour, which may introduce selection bias or confounding [28,29].

Confounding of the relationship between vaccine receipt and COVID-19 outcomes may be very likely, and spurious relationships between vaccine receipt and implausible outcomes have been noted in other studies comparing vaccine recipients to non-recipients. The use of eligibility criteria to define comparable exposure groups, covariates

based on updated subject-matter knowledge will allow investigators to adequately address confounding through the design and analysis.

The baseline clinical history of individuals in the initial priority groups (i.e. health care workers and people living in nursing home) may not be systematically included in BIFAP eHR. Thus, many of them may not be up-to-standard for research as explained above and power limitation may be expected.

Even though efforts will be done for proper control of bias and multivariate adjustment minimizing confusion, no information about the job and type of residence will be available. Consequently, confusion may still be present due to the higher probability of infection among them versus other social groups. That aspect would direct towards a reduction in the effectiveness estimations.

If data about determinants, such as personal health-seeking behaviour, would not be recorded in the database, the selection of patients included in the compared groups and/or their dates to start the comparison could be biased, i.e.

- Patients prone to infections or to develop a severe/hospitalised infection or those with active respiratory infection/disease (prevalent active pneumonia, COPD, etc) decided to attend to receive the vaccination earlier/more than those less prone to it, we could observe patients more affected by covid among the vaccinated group. That aspect would direct towards a biased lower effectiveness estimation due to selection bias).

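### The hazard ratio for days 0-14 after dose 1 is presented as locating the start of vaccine effect, when it should be declared a check for selection bias that is expected to be near 1

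*Protocol*

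**What the plan says.** - **Time windows.** Section 9.1.1.4 divides the span from dose 1 to 14 days after dose 2 "In order to properly observe the moment when the effect of the vaccination starts". The first window is "D1-induction time: up-to 14 days after 1"; the D1-effectiveness window starts at day 15. The main analysis, by brand, begins 15 days or more after completion: "days after full vaccination series whether 1- or 2-doses regimens".
- **Estimation.** Section 9.7.3.1 fits Cox models for each window, including days 0-14 after dose 1, and takes effectiveness as 1 minus HR.
- **Comparators.** Under sections 9.1.1.4 and 9.3.1, time zero is the day dose 1 is given. Ten people unvaccinated at that date are drawn at random, matched on birth cohort, sex and region. Section 9.3.3.1 dates a case by its sample date.
- **Study-size criterion.** Section 9.5 tabulates the chance that the upper 95% limit of the RR is below 1, described as "a correlate of the lower bound of the vaccine effectiveness estimate being above 0.00" and as "demonstrating a protective effect of vaccination".
- **Bias.** Section 7 names confounding as the likely strongest threat to validity. Section 9.9 adds that "spurious relationships between vaccine receipt and implausible outcomes have been noted in other studies comparing vaccine recipients to non-recipients". Section 9.7.4.1 offers calendar-month strata: "Stratifying by months, we could observe differences in effectiveness that could be affected by a higher confusion in months".

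**The concern.** In the first days after dose 1 little or no vaccine effect is expected, as the label induction time concedes. If the HR there is below 1, the first explanation to examine is selection. A person who is symptomatic, isolating or awaiting a result may put off dose 1 and can still be drawn that day as an unvaccinated comparator. If that person's positive sample follows, it counts as an early event in the unvaccinated group only. Matching on birth cohort, sex and region does not prevent this.

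The only purpose the protocol gives for comparing these windows is to see when the effect starts. Nowhere does it say that an early HR below 1 would point to bias. Section 9.1.1.5 has a heading about assessing unmeasured confounding, but it lists matching, adjustment and head-to-head comparison, which reduce confounding and do not measure what remains.

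The early HR may thus be read as early onset of effect. Selection that persists into later windows would also inflate the effectiveness figures, and no stated check would show it.

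**Working it through.** **Inputs from the protocol.** Outcome risk 0.0006057 in 14 days (section 9.5); 7,720,843 people and ratios 1:1 and 2:1 (Table 1); 10:1 matching (section 9.3.1); windows 0-14 and 15-90 days (section 9.7.3.1).

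**Assumptions.** The protocol gives neither the size of any bias nor the number of vaccinees per brand. I take a vaccine with no effect (true RR 1), an observed RR equal to a bias of 0.90 (0.95 and 0.80 for range), and 250,000, 500,000 or 1,000,000 vaccinees. Risk for days 15-90 is scaled at a constant rate: 0.0006057 × 76/14 = 0.003288.

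**Formula.** With risks p1 (vaccinated) and p0 (unvaccinated) and group sizes n1 and n0:

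SE² = (1 − p1)/(n1·p1) + (1 − p0)/(n0·p0)

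P(upper 95% limit < 1) = Φ(−ln RR / SE − 1.96)

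**Step 1: the plan's own figure.** Table 1 gives probability 1 in every row. For its weakest assumed effect (Janssen, RR 0.331, 1:1), expected events are 774 and 2,338 and SE = 0.0415. Then 1.1056/0.0415 = 26.7, and the probability is 1. All rows of Tables 1 and 2 reproduce.

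**Step 2: no vaccine effect, Table 1 inputs, 1:1.** The probability is 2.5% with no bias, 41% at bias RR 0.95 and 94% at 0.90. Table 1 gives each brand the whole adult database, so these are upper-end figures.

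**Step 3: no vaccine effect, 10:1 by brand.** Worked case, 250,000 vaccinees, days 0-14, bias RR 0.90:
- Events: 250,000 × 0.0006057 × 0.90 = 136.3 vaccinated; 2,500,000 × 0.0006057 = 1,514 unvaccinated.
- SE = 0.0894; 0.1054/0.0894 = 1.178.
- Φ(1.178 − 1.96) = Φ(−0.782) = 22%.

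Same case, days 15-90: 739.8 and 8,220 events, SE = 0.0383, 0.1054/0.0383 = 2.749, Φ(0.789) = 78%.

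| Vaccinees | Days 0-14, RR 0.95 | RR 0.90 | RR 0.80 | Days 15-90, RR 0.95 | RR 0.90 |
|---|---|---|---|---|---|
| 250,000 | 9% | 22% | 66% | 28% | 78% |
| 500,000 | 13% | 38% | 92% | 49% | 97% |
| 1,000,000 | 22% | 65% | 99.7% | 78% | >99.9% |

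**Step 4: is the early HR precise enough to be a check?** With true HR 1 and 250,000 vaccinees, events are 151.4 and 1,514 and SE = 0.0852, so the 95% interval is exp(±1.96 × 0.0852) = 0.85-1.18. With 1,000,000 vaccinees SE = 0.0426 and the interval is 0.92-1.09.

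**Limits.** These are risk-ratio approximations without censoring. At 1,000,000 vaccinees, 10:1 needs 10,000,000 comparators, more than the 7,720,843 adults, so comparators would be reused and intervals somewhat wider. The risk input counts symptomatic cases only, while the main outcome is any confirmed infection, so real event counts may be higher.

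**The case against.** A reader might infer that the protocol has two success rules and that both would be met for a useless vaccine. The text does not support that:
- The lower-bound-above-0 criterion stands only in the study-size section. Section 9.7.3.1 sets no threshold, and the onset-of-effect reading has none either.
- Days 0-14 are labelled induction and lie outside the main analysis. The purpose sentence covers the whole span to 14 days after dose 2, so a claim of early effect is something the wording invites, not something it states.
- The checklist in Annex 1 gives trial efficacy as the prior hypothesis. A null vaccine with bias RR 0.90 would show about 10% effectiveness, far from the 63.7% to 95.6% in Tables 1 and 2.
- At 250,000 to 500,000 vaccinees a 10% bias meets the criterion in days 0-14 in only 22-38% of cases.

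The plan also has partial safeguards: health care use in the two weeks up to time zero and COVID-19 test counts (section 9.3.4), an influenza-vaccinated stratum and monthly strata (9.7.4.1), head-to-head brand comparisons (9.1.1.5), exclusion of prior infection (9.3.1), and the option of description only if confounding is insurmountable (9.9).

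All of this stands, and it limits the point. It does not remove it. None of these safeguards has an expected null value against which residual bias could be seen. Monthly strata cannot separate confounding from a real change in effectiveness, and they miss confounding that is constant over months. Nor can the point simply be left to a statistical analysis plan, because the protocol itself fixes the purpose of the early comparison and the meaning given to a lower bound above 0.

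**Conclusion.** The concern holds in a limited form. The protocol gives the early comparison the wrong stated purpose and assigns no check for residual selection, although it already estimates an HR that could serve as one. The wording in section 9.5 is too strong: at bias RR 0.90, a null vaccine meets the criterion in 78% to >99.9% of cases for days 15-90 and 22% to 65% for days 0-14, over 250,000 to 1,000,000 vaccinees per brand. These figures rest on assumed bias and brand sizes and on constant risk over time. They show how sensitive the criterion is; they do not show that bias of this size is present. The change is worth making before results are seen, so that the early HR is not interpreted after the fact.

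**What to change.** 1. In sections 9.1.1.4 and 9.7.3.1, state that the HR for days 0-14 after dose 1, or an earlier part of that window with the cut justified, is a negative-control window expected near 1. Report it by brand, and by month of time zero where numbers allow, next to the effectiveness estimate. Read a departure from 1 as possible selection bias, not as onset of effect.
2. Add a sensitivity analysis that starts follow-up of both members of each matched set after that window.
3. In section 9.5, replace the statement that a lower bound above 0 demonstrates protection. Say instead that effectiveness is interpreted by its estimate and confidence interval together with the negative-control HR.

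**Cost.** Wording and a few model terms; no new data. The check has limits: its interval is wide for small brands (about 0.85-1.18 at 250,000 vaccinees), opposing biases may cancel and leave an HR near 1, and early bias may differ from later bias. It should therefore inform interpretation and not be used to correct the estimates or as a condition for reporting them.
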